#### 2.3.4.1.4 Subgroup Analysis

Subgroup analyses will be conducted for the primary endpoint for the following factors:

Key subgroup analyses:

- Age (< median age value,  $\geq$  median age value)
- Sex (male, female)
- Race (White, Black or African American, Asian, and Other (American Indian or Alaska native + Not reported + Unknown + multiple).
- Region (North America, Latin America, Europe, other)
- Use of SGLT2 at baseline (Yes, No)
- Baseline BMI categories (<median BMI value,  $\geq$  median BMI value)
- Duration of diabetes (< 10,  $\geq$ 10 years)
- Baseline HbA1c categories (<8%,  $\geq$ 8%)
- Baseline eGFR categories (<median eGFR value,  $\geq$  median eGFR value)
- Baseline metformin use (Yes, No)
- History of CV disease (CVD) (yes, no)

Other subgroup analyses:

- Age ( $<65$ ,  $\geq 65$  and  $<75$ ,  $\geq 75$  years)
- Randomization strata of SGLT2 use (Current use, Potential future use, Neither current nor potential future use)
- Baseline BMI categories ( $<30$ ,  $\geq 30$  to  $<40$ ,  $\geq 40$  kg/m^2)

- Ethnicity (Hispanic, not Hispanic)
- Baseline eGFR categories ( $< 30 \text{ mL/min/1.73m}^2$ ,  $30 \text{ to } < 60 \text{ mL/min/1.73m}^2$ ,  $60 \text{ to } < 90 \text{ mL/min/1.73m}^2$ ,  $\geq 90 \text{ mL/min/1.73m}^2$ )

Each of these factors will be analyzed statistically using a Cox proportional hazard model including the effects of the primary analysis model and effects for subgroup and subgroup-by-treatment interaction. The incidence rate, estimated hazard ratios between pooled efpeglenatide and placebo, and associated 95% confidence intervals will be calculated within each of the subgroups generated by these analyses. Subgroup by treatment interaction p-values will be reported, and results will be plotted using forest plot.

#### **2.3.4.2 Analyses of secondary efficacy endpoints**

If the NI with the 1.8 and 1.3 margin is demonstrated on the primary endpoint, the superiority of pooled efpeglenatide vs placebo for the primary endpoint will be tested in a hierarchical order. The superiority will be claimed if the UB of the 2-sided 95% CI of hazard ratio is less than 1. The nominal p-value using the log-rank test (stratified by randomization stratum of use of an SGLT2 inhibitor) will also be calculated.

The secondary time to event endpoints will be analyzed using the same Cox proportional hazards model as used for the analysis of primary endpoint described above. The analyses will be performed by including events positively adjudicated by the CEC for cardiac events, and events as reported by investigator for renal events. The hazard ratios between pooled efpeglenatide and placebo will be estimated along with the associated 2-sided 95% CIs. See [Appendix C](#) for the censoring rule.

Kaplan-Meier curves of the cumulative incidence rates will be provided by treatment groups. The incidence rate per 100 patient-years will be reported. The p-value using the log-rank test (stratified by randomization stratum of use of an SGLT2 inhibitor) will also be calculated.

Individual components of the secondary endpoints will be analyzed using the same Cox proportional hazards model described above.

In addition, the total number of events sent for adjudication and positively adjudicated will be summarized as well as the concordance rate between investigator opinion and adjudication by the CEC for each cardiac event type.

#### **2.3.4.3 Exploratory efficacy analyses**

Time to event endpoints will be analyzed using the same model described for the secondary primary endpoints.

For continuous efficacy endpoints, summary statistics at scheduled visits using observed data will be provided for each treatment group. The summary will include the number of observations, mean, SD, SE, minimum, median, and maximum. Graphical presentations will be used to examine trends over time using mean values ( $\pm \text{SE}$ ) and mean changes from baseline ( $\pm \text{SE}$ ) at each scheduled visit.

In addition, Kaplan-Meier plot of time to initiation of SGLT2 use will be provided. See [Section 2.5.3](#) for handling missing medication dates. Patients on SGLT2 at baseline will be censored at randomization. Patients who never start SGLT2 will be censored at the patients of end of study date (refer to [Section 2.1.4](#)).

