9.4.3 Other analyses

Exploratory analyses will be described in the statistical analysis plan finalized before DB lock.

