### 1.2.3 Tertiary/Exploratory objectives

- To compare efpeglenatide versus placebo on the occurrence of the following events in T2DM patients with high CV risk:
  - CV death;
  - Stroke (fatal and non-fatal);
  - Myocardial infarction (MI) (fatal and non-fatal);
  - All cause death;
  - Hospitalization for unstable angina;
  - Hospitalization for Heart Failure (HHF);
  - Coronary revascularization procedures (percutaneous coronary intervention [PCI] or coronary artery bypass graft [CABG]).
- To compare efpeglenatide versus placebo on the following endpoints:
  - Change in hemoglobin A1c (HbA1c);
  - Change in body weight;
  - Change in blood pressure (BP);
  - Change in Urinary Albumin-Creatinine Ratio (UACR).
- To compare efpeglenatide versus placebo on immunogenicity.

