### **2.1.3.3 Exploratory efficacy endpoint(s)**

The exploratory efficacy endpoints are:

- Time to CV death
- Time to first occurrence of Stroke (fatal and non-fatal)
- Time to first occurrence of MI (fatal and non-fatal)
- Time to all cause death
- Time to first occurrence of hospitalization for unstable angina
- Time to first occurrence of HHF
- Time to first occurrence of coronary revascularization procedures (PCI or CABG)
- Changes from Baseline to scheduled visits per protocol in:
  - HbA1c
  - Body weight
  - BP
  - UACR
  - Heart rate

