#### **2.3.4.4 Multiplicity issues**

A hierarchical testing procedure will be used to strongly control the overall Type-1 error rate at 2-sided 0.05 (0.025 for 1-sided).

The primary hypotheses will be tested first with below fixed sequence, each at alpha=0.05 (2-sided) level:

1. Non-inferiority of efpeglenatide (pooled 4 mg + 6 mg) versus placebo on 3-point MACE with NI=1.8
2. Non-inferiority of efpeglenatide (pooled 4 mg + 6 mg) versus placebo on 3-point MACE with NI=1.3

If the hypotheses above are statistical significant, the secondary hypotheses will be tested in below fixed sequence with each testing at significance level of 0.05 (2-sided) to continue to control the overall family-wise error rate at 0.05 (2-sided):

- Superiority for 3-point MACE
- Superiority for expanded MACE
- Superiority for the new or worsening nephropathy

Inferential conclusions about successive secondary hypotheses require statistical significance of the prior one. No further multiplicity adjustments will be made for other efficacy endpoints or subgroup analyses for which nominal p-values may be provided for descriptive purpose only.

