### ***General common rules***

All safety analyses will be performed on the safety population as defined in [Section 2.2.4](#), unless otherwise specified, using the following common rules:

- Safety data in patients who do not belong to the safety population (e.g., exposed but not randomized) will be listed separately
- For WBC and differential counts, the baseline is defined as the last available value before the first injection of IMP where no differential component is missing.
- The potentially clinically significant abnormality (PCSA) values are defined as abnormal values considered medically important by the Sponsor according to predefined criteria/thresholds based on literature review and defined by the Sponsor for clinical laboratory tests, vital signs, and ECG (PCSA version dated May 2014 [[Appendix A](#)])
- PCSA criteria will determine which patients had at least 1 PCSA during the on-treatment period, taking into account all evaluations performed during the on-treatment period, including unscheduled or repeated evaluations. The number of all such patients will be the numerator for the on-treatment PCSA percentage
- The treatment-emergent PCSA denominator by group for a given parameter will be based on the number of patients assessed for that given parameter during the on-treatment period by treatment group in the safety population.
- For laboratory and vital sign parameters defined as efficacy endpoints, descriptive statistics and graphs will be provided in the efficacy section only, and PCSAs summaries will be provided in the safety section.
- For quantitative safety parameters based on central laboratory/reading measurements, descriptive statistics will be used to summarize results and change from baseline values by visit and treatment group. Summaries will include the last on-treatment value. The last on-treatment value is defined as the value collected on the same day/time of the last injection of IMP. If this value is missing, this last on-treatment value will be the closest value prior to the last injection of IMP.
- The analysis of the safety variables will be essentially descriptive, and no statistical hypothesis testing is planned.

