#### **2.5.6 Pooling of centers for statistical analyses**

Center will not be included in the statistical models for efficacy analyses. However, all centers within a region will be pooled, and region will be included as a fixed factor in a parametric statistical model (e.g., Cox proportional hazards model, etc.) for primary and secondary efficacy endpoints.

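### The objective is to compare efpeglenatide with placebo on change in HbA1c, body weight, BP and UACR, but the SAP pre-specifies no between-group estimate, CI or baseline adjustment, and no scale for UACR

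*SAP*

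**What the plan says.** Protocol Table 2 and SAP 1.2.3 state the same tertiary/exploratory objective: "To compare efpeglenatide versus placebo on the following endpoints". The list that follows is change in HbA1c, body weight, BP and UACR. The protocol gives no method and passes the question on in 9.4.3: "Exploratory analyses will be described in the statistical analysis plan finalized before DB lock".

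SAP 2.1.3.3 defines the endpoints, adding heart rate to the list: "Changes from Baseline to scheduled visits per protocol in". SAP 2.3.4.3 then supplies the only analysis: "For continuous efficacy endpoints, summary statistics at scheduled visits using observed data will be provided for each treatment group". It continues: "The summary will include the number of observations, mean, SD, SE, minimum, median, and maximum". Means and mean changes from baseline, each with SE, are to be plotted by visit. SAP 2.3 says that descriptive summaries appear by 4 mg, 6 mg, pooled efpeglenatide and placebo.

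**The concern.** An objective worded as a comparison should lead to a stated estimate of the difference and its uncertainty. Here the protocol defers the method to the SAP, and the SAP stops at by-arm description. The same SAP section gives the exploratory time-to-event endpoints the Cox model, and with it a hazard ratio and CI, so the two kinds of exploratory endpoint are treated unequally without explanation.

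Three things are at stake:

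- **Pre-specification.** Any model chosen after unblinding to report these differences would be post hoc.
- **Who contributes.** Observed-data means at each visit describe whoever attended. Planned follow-up ranges from 24 to 36 months, so later visits hold only earlier enrollees. Participants who refuse site visits are followed by telephone (Protocol 7.1.1), which yields no laboratory values. The Schedule of Activities shows HbA1c and spot UACR at closeout for participants still on IMP, but not for those who stopped early.
- **UACR scale.** UACR is usually strongly right-skewed. If no transformation is applied, a few very high values drive its mean and SE.

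**Working it through.** The documents give no SD, sample size or power for these endpoints, so there is no stated figure to reproduce. The first step is textual. The others are illustrations on assumed inputs.

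**1. Does another section fill the gap?**

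- SAP 2.5.6 limits the modelling statement: "region will be included as a fixed factor in a parametric statistical model (e.g., Cox proportional hazards model, etc.) for primary and secondary efficacy endpoints". Exploratory endpoints are not named.
- SAP 2.3.4.4 mentions other efficacy endpoints, "for which nominal p-values may be provided for descriptive purpose only". It names no test, estimate or CI.
- The safety rules send these parameters back: "For laboratory and vital sign parameters defined as efficacy endpoints, descriptive statistics and graphs will be provided in the efficacy section only".
- Appendix B has no row for the continuous endpoints.
- The multiple imputation and tipping-point work in SAP 2.3.4.1.3 covers MACE only. SAP 2.5.3 leaves a change score missing if either value is missing.
- For UACR, the only numerical rule is in SAP 2.5.1, which exempts it from the substitution for values beyond the quantification limits. No log scale, geometric mean or ratio to baseline appears.

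Nothing fills it.

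**2. What can be derived from the planned tables?** With pooled and placebo means and SEs side by side, the crude difference is mean(pooled) − mean(placebo), with SE = √(SE²pooled + SE²placebo). Randomization 1:1:1 of about 4000 gives about 2667 versus 1333, and √(1/2667 + 1/1333) = 0.0335. The 95% half-width with complete data is 1.96 × SD × 0.0335:

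| Endpoint | Assumed SD of change | Half-width |
|---|---|---|
| HbA1c (points) | 1.0 to 1.5 | 0.07 to 0.10 |
| Body weight (kg) | 4 to 6 | 0.26 to 0.39 |
| Systolic BP (mmHg) | 14 to 18 | 0.9 to 1.2 |

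A crude comparison would therefore be fairly precise at this sample size.

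**3. What does baseline adjustment add?** With equal variances σ² at baseline and follow-up and correlation ρ, the change-score variance is 2σ²(1 − ρ) and the adjusted variance is σ²(1 − ρ²). The ratio is (1 + ρ)/2, which is 0.70, 0.75 and 0.85 at assumed ρ of 0.4, 0.5 and 0.7. Adjustment thus removes 15% to 30% of the variance. Half-widths shrink by 1 − √0.85 = 8% to 1 − √0.70 = 16%.

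**4. Does the UACR scale matter?** Assume lognormal follow-up values with log-SD s in both arms, a geometric mean ratio of 0.80 and 2:1 allocation, with n participants on placebo.

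- Untransformed means: z² = n × 0.20² / [(e^(s²) − 1)(1 + 0.80²/2)] = n × 0.04 / [1.32(e^(s²) − 1)]
- Log scale: z² = n × (ln 0.80)² / [s²(1 + 1/2)] = n × 0.0498 / (1.5 s²)
- Relative efficiency: 0.913 × s² / (e^(s²) − 1)

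This gives 0.913 × 1/1.718 = 53% at s = 1.0, 0.913 × 2.25/8.488 = 24% at s = 1.5, and 0.913 × 3.24/24.53 = 12% at s = 1.8.

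These figures compare follow-up levels, whereas the endpoint is change. A simulation of change used 1333 versus 2667 participants, median 30 mg/g, baseline log-SD 1.2 to 2.0, log-change SD 0.8 to 1.0 and a true ratio of 0.80, all assumed except the allocation. A difference in untransformed mean change was detected in 20% to 93% of 1000 trials per setting. A log-scale difference was detected in essentially all. The placebo mean was about 3 to 12 times the median (85/30 to 359/30).

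**The case against.** The strongest reply is that an exploratory objective to compare can be met descriptively. SAP 2.3 puts pooled efpeglenatide and placebo side by side, the arms are randomized, and step 2 shows that the crude difference is precise. A chance baseline imbalance has an SE of only about 0.034 SD. Assumed study discontinuation is 2% a year, and participants who stop IMP are asked to keep attending visits. Albuminuria also gets an inferential comparison elsewhere, because macroalbuminuria with a UACR rise of at least 30% is a component of the secondary renal endpoint and is analysed by Cox model.

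Much of this stands. A reader might infer that the trial cannot answer the objective as written. The documents do not support that: a crude difference and CI follow from the planned tables, and nominal p-values are permitted. A reader might also infer that the UACR tables would say nothing about a typical participant. That fails too, because the median is among the listed statistics. The untransformed scale is itself inferred from silence; the SAP names no scale.

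Three things remain. The estimate and its method are not pre-specified. The crude difference ignores baseline and rests on changing subsets of participants. The planned UACR plots show means with SE, where the median gives no help. Nor does the SAP say that description was a deliberate choice: it rules out hypothesis testing explicitly for safety and for ADA data, but not here.

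**Conclusion.** The point holds as a gap in pre-specification and a weaker method than the data allow. It is worth fixing but not critical. No between-group estimate, CI or baseline adjustment is planned for change in HbA1c, body weight, BP or UACR, and no transformation is stated for UACR.

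The reach is limited. These endpoints are outside the hierarchy in SAP 2.3.4.4, so a reader should not infer any effect on the MACE, expanded MACE or nephropathy conclusions, or on type I error. For HbA1c, weight and BP the precision gain is modest: 15% to 30% of the variance at an assumed correlation of 0.4 to 0.7. For UACR the choice of scale matters more, but the 53%, 24% and 12% efficiencies rest on a lognormal model, assumed log-SDs and an assumed 20% effect. The textual finding depends on none of these figures. Heart rate has the same gap but is not in the comparison objective.

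**What to change.** Add to SAP 2.3.4.3, before database lock:

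- **HbA1c, body weight and BP** (heart rate optional): a repeated-measures mixed model for change from baseline with treatment at three levels, visit, treatment-by-visit, baseline, baseline-by-visit, region and SGLT2 stratum. ANCOVA at a named visit, without the visit terms, would also serve. State the covariance structure if the mixed model is used.
- **Reporting:** the pooled efpeglenatide versus placebo difference with 95% CI at named visits. Weeks 48 and 96, for example, are scheduled on site and fall within the minimum planned follow-up of 24 months.
- **Data used:** state how values after IMP discontinuation are handled. Also say whether values after changes in background glucose-lowering therapy are included, since this affects what an HbA1c difference means.
- **UACR:** the same model on log(UACR), reported as geometric mean ratios. Give a rule for values below quantification, because SAP 2.5.1 exempts UACR from the existing one.
- **Status:** label p-values nominal, keep the descriptive tables, and add a row to Appendix B.

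The cost is SAP wording and a few model outputs, with no new data and no alpha. The downside is that the mixed model relies on a missing-at-random assumption, which the text should state.

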#### **2.3.4.4 Multiplicity issues**

A hierarchical testing procedure will be used to strongly control the overall Type-1 error rate at 2-sided 0.05 (0.025 for 1-sided).

The primary hypotheses will be tested first with below fixed sequence, each at alpha=0.05 (2-sided) level:

1. Non-inferiority of efpeglenatide (pooled 4 mg + 6 mg) versus placebo on 3-point MACE with NI=1.8
2. Non-inferiority of efpeglenatide (pooled 4 mg + 6 mg) versus placebo on 3-point MACE with NI=1.3

If the hypotheses above are statistical significant, the secondary hypotheses will be tested in below fixed sequence with each testing at significance level of 0.05 (2-sided) to continue to control the overall family-wise error rate at 0.05 (2-sided):

- Superiority for 3-point MACE
- Superiority for expanded MACE
- Superiority for the new or worsening nephropathy

Inferential conclusions about successive secondary hypotheses require statistical significance of the prior one. No further multiplicity adjustments will be made for other efficacy endpoints or subgroup analyses for which nominal p-values may be provided for descriptive purpose only.

#### **2.3.5 Analyses of safety data**

The summary of safety results will be presented by treatment group. All safety analyses will be performed on the safety population. The AE analysis will exclude the CV events reported and final diagnosed as CV events by investigator and also positively adjudicated as CV events by CEC.

In addition to the on-treatment period, all AEs, SAEs, AEs leading to permanent treatment discontinuation, and AEs leading to death will be summarized for the on-study period as defined in [Section 2.1.4](#).

### ***General common rules***

All safety analyses will be performed on the safety population as defined in [Section 2.2.4](#), unless otherwise specified, using the following common rules:

- Safety data in patients who do not belong to the safety population (e.g., exposed but not randomized) will be listed separately
- For WBC and differential counts, the baseline is defined as the last available value before the first injection of IMP where no differential component is missing.
- The potentially clinically significant abnormality (PCSA) values are defined as abnormal values considered medically important by the Sponsor according to predefined criteria/thresholds based on literature review and defined by the Sponsor for clinical laboratory tests, vital signs, and ECG (PCSA version dated May 2014 [[Appendix A](#)])
- PCSA criteria will determine which patients had at least 1 PCSA during the on-treatment period, taking into account all evaluations performed during the on-treatment period, including unscheduled or repeated evaluations. The number of all such patients will be the numerator for the on-treatment PCSA percentage
- The treatment-emergent PCSA denominator by group for a given parameter will be based on the number of patients assessed for that given parameter during the on-treatment period by treatment group in the safety population.
- For laboratory and vital sign parameters defined as efficacy endpoints, descriptive statistics and graphs will be provided in the efficacy section only, and PCSAs summaries will be provided in the safety section.
- For quantitative safety parameters based on central laboratory/reading measurements, descriptive statistics will be used to summarize results and change from baseline values by visit and treatment group. Summaries will include the last on-treatment value. The last on-treatment value is defined as the value collected on the same day/time of the last injection of IMP. If this value is missing, this last on-treatment value will be the closest value prior to the last injection of IMP.
- The analysis of the safety variables will be essentially descriptive, and no statistical hypothesis testing is planned.

